The participant will be contacted by phone within 24-72 hours after baseline visit 2 discharge to ensure no adverse events have occurred on both biopsy and arterial line sites.

Intervention Period (Weeks 1-12)

Biopsy and catheter insertion site check: A biopsy site and catheter site check will be done when the participants pick up their first supply of ${}^{2}H_{2}O$.

H₂O Administration and Return (12-week labelling period) and Urine Collections: ²H₂O will be prepared by the Mass Spectrometry Core. Participants will receive 50 mL aliquots of 70% ²H₂O or 35 mL aliquots of 99.9% ²H₂O in individual amber prescription containers. Participants will drink three 35 mL or 50 mL doses per day for the first week, and two doses per day from the second through the twelfth week. Participants will receive the ²H₂O aliquots containers bi-weekly, a log sheet to record consumption, and at-home urine collection cups with instructions. Participants will be instructed to keep urine samples taken at home in the refrigerator until their next in-person visit (every other week). Urine samples will be used to verify compliance weekly (at AH TRI or PBRC). Compliance with ²H₂O intake for both groups will be monitored through the weekly urine collections and return of empty containers for counting. ²H enrichments in urine, reflecting ²H body water enrichments, will be measured by isotope ratio mass spectrometry. Enrichments are expected to be between 1-2.5%. If a participant's urine sample is <1%, the study team will encourage compliance with the participant. If enrichment is <1% for a period of 3 weeks, the PIs will discuss participant withdrawal. Participants will be instructed to maintain their normal daily and weekly routines.

Participants in the EX group will engage in 12-week endurance exercise training.

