It is very unlikely that severe hypoglycemia will occur during the insulin infusion because blood glucose will be monitored every 5 to 10 minutes at the bedside and glucose infusions of 20% dextrose will be adjusted to maintain euglycemia (plasma glucose ~ 90 mg/dl). The participant is also kept awake at all times during the insulin infusion so that they can report or be observed for any changes. If the participant's blood glucose is nearing hypoglycemic levels, the plasma glucose will be checked even more frequently, and the 20% dextrose infusion rate increased. If hypoglycemia occurs, the insulin infusion will be discontinued, and intravenous glucose continued at higher rates along with the intake of oral carbohydrates. The volunteers will then be monitored for at least 2 hours during the IV glucose infusion and oral supplementation, then for at least 1 hour after discontinuing the IV glucose. Additionally, there will be in-house supervision by a qualified physician or mid-level provider at all times during the procedure and immediate availability of corrective measures (IV 50% dextrose and/or glucagon).

Resting Metabolic Rate/Respiratory Quotient (RMR/RQ): A member of the study staff will remain with the subject at all times to ensure his/her comfort.

Surveys: Surveys will be offered via password protected computer-based software REDCap. IP addresses will not be collected. Survey results will be aggregated, no individual responses will be shared. Participants may opt out of survey questions they develop discomfort with.

Provisions to Protect the Privacy Interest of Subjects

Participants will be assigned unique identifiers for study-related records. All precautions will be taken to make sure that only authorized individuals will access participant research records. The collection of sensitive information about participants will be limited to the minimum necessary to achieve the aims of the research, so that no unneeded sensitive information will be collected.

 Current Version Date:
 08/05/2024
 IRBNet #: 1805407

 Page 33 of 42

Early Withdrawal of Subjects

Investigator Withdrawal of Subjects

The participation in this study may be stopped at any time by the study PI without the participant's consent because:

- The study medical investigator thinks it necessary for subject's health or safety;
- Participant has not followed study instructions;
- The AdventHealth Translational Research Institute has stopped the study;

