- Administrative reasons require the participant's withdrawal;
- Participant is unable to complete a procedure;
- We are unable to place a venous line or place a catheter for the subcutaneous microdialysis.

Subject Request for Withdrawal from Study

Participation in this study is voluntary. Participants may decide not to participate in this study or may withdraw from this study at any time without penalty or loss of benefits. If a participant leaves the study before the final regularly scheduled visit, she/he may be asked by the study doctor to make a final visit for some 'end-of-study' procedures. This is to make sure that there are no safety concerns

Data Collection and Follow-up for Withdrawn Subjects

Participants who request withdrawal or who are withdrawn by the PI from the study will have their data maintained in the research database up to the point of withdrawal. The available data will be included in subsequent analysis because keeping these participants in the analysis is essential for study validity.

Adverse Events - Recording and Reporting

Each participant will be evaluated for adverse events at every study visit. Any event that is reported to the study staff and which meets the criteria of an adverse event will be documented as such and graded as to its attribution (unrelated to protocol, or possibly, probably, or definitely related to protocol) and severity (mild, moderate, or severe). Any severe and/or unanticipated adverse event will be immediately reported to the IRB according to AdventHealth IRB guidelines.

At each contact with the subject, the study team will seek information on adverse events by specific questioning and, as appropriate, by the Provider through examination. Information on all adverse events will be recorded immediately in the source document, also in the appropriate adverse event module of the case report form CRF. All clearly related signs, symptoms, and abnormal diagnostic procedures results

will be recorded in the source document. All adverse and unexpected events will be reported according to AdventHealth IRB guidelines.

Safety Monitoring Plan

Safety Monitoring

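### After randomisation the PI may end all study participation for undefined non-compliance or a failed secondary procedure, so the primary outcome goes unmeasured, with more scope for this in the exercise arm

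*Protocol*

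**What the plan says.** **Grounds for removal.** Under Investigator Withdrawal of Subjects, the list of reasons opens with "The participation in this study may be stopped at any time by the study PI without the participant's consent because". What is stopped is participation in the study, not only training or one procedure. Three non-safety grounds matter here: "Participant has not followed study instructions", "Participant is unable to complete a procedure" and "We are unable to place a venous line or place a catheter for the subcutaneous microdialysis". None has a definition or threshold.

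**Label enrichment.** The Intervention Period section adds: "If enrichment is <1% for a period of 3 weeks, the PIs will discuss participant withdrawal".

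**Timing.** Randomisation is at Visit 1 (day -14), once the VO₂max test is done. The Visit 2 catheters, the labelled water and the training all come later.

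**After withdrawal.** Under Data Collection and Follow-up for Withdrawn Subjects, data up to withdrawal are retained, and "The available data will be included in subsequent analysis because keeping these participants in the analysis is essential for study validity". Under Subject Request for Withdrawal from Study, a person who leaves early "may be asked by the study doctor to make a final visit for some 'end-of-study' procedures". The stated purpose of that visit is safety, and no adipose biopsy is specified.

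**The concern.** The retention sentence and the withdrawal grounds pull against each other. Analysing what is available helps only if the outcome has been measured, and here it is measured after the point at which most of these removals would occur.

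Two consequences follow.

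- **Selective loss.** Non-compliance is judged at discretion and has more opportunities to arise in EX. Removing poor adherers there moves the comparison away from the groups as randomised, towards adherent exercisers against all controls. If adherence is related to outcome, this can create an apparent benefit where none exists.
- **Avoidable loss.** Microdialysis serves a secondary outcome. A failed microdialysis catheter at Visit 2 can nevertheless end follow-up for someone whose primary outcomes could still be measured.

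**Working it through.** **1. The plan's own attrition figure.** The Sample Size section expects about 17% loss: 70 × (1 − 0.17) = 58.1, which reproduces the stated 58 (29 per arm). The allowance is 70 − 58 = 12 participants.

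**2. What a removed participant can contribute.** Labelled water begins in week 1, after the day -7 biopsy. The only later biopsy is on day 88 (Visit 4). A participant removed in between has:
- no labelled sample for adipocyte formation ('f') or TG turnover;
- no post-intervention snRNAseq or histology.

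All four primary outcomes are defined as pre and post assessments. The tests named in the Statistical Analysis Plan section are paired pre-post tests, which need both biopsies. The retained data therefore cannot supply the primary outcome.

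**3. Which grounds can differ by arm.**

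| Ground | Link to arm in the protocol |
|---|---|
| Instructions not followed | EX alone has training: 3 sessions × 12 weeks = about 36. Both arms have labelled water, urine collections and weight maintenance. |
| Line or microdialysis catheter at Visit 2 | None shown; the intervention has not started. |
| Microdialysis catheter at Visit 4 | Little at stake; the Respiratory Quotient section puts the biopsy before these catheters. A failed venous line could come before the biopsy. |
| Enrichment below 1% for 3 weeks | None shown; monitored alike in both groups, and leads to a discussion only. |

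**4. Size of selective loss.** The protocol gives no removal rate, so this is an illustration under assumptions:
- no true effect;
- SD 6.0 points (the protocol's baseline SD of 'f', used here for the analysed outcome);
- 29 CTRL completers;
- 35 EX participants, of whom the k least adherent are removed;
- correlation r between adherence and outcome.

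Bias = −r × 6.0 × m, where m is the absolute mean of the lowest 35 − k of 35 ordered standard normal values. By simulation m = 0.164, 0.298 and 0.423 for k = 3, 6 and 9. For example, 0.3 × 6.0 × 0.164 = 0.30 and 0.5 × 6.0 × 0.423 = 1.27. Type I error comes from simulated two-sample t tests at a two-sided 5% level.

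| EX removed (k) | Bias favouring exercise, points of 'f' (r = 0.3 to 0.5) | Two-sided type I error |
|---|---|---|
| 3 | 0.3 to 0.5 | about 5.5% to 6% |
| 6 | 0.5 to 0.9 | about 6% to 9% |
| 9 | 0.8 to 1.3 | about 8% to 13% |

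**5. Power.** The target difference in change and its SD are not stated. A difference of 17.8 − 11.4 = 6.4 points with an SD of change of 6.0 × √2 = 8.49 (zero pre-post correlation assumed) gives 80.6% with 29 per arm, close to the stated 80%. Losses beyond the planned 17% lower this to about 79% (2 more lost), 76% (6 more) and 71% to 73% (10 more). With SD 6.0 instead, power is still 94% to 95% with 10 more lost.

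**The case against.** The strongest reply is that the wording is permissive, that collected data are kept and analysed, and that the instructions ground is not confined to EX. CTRL participants can also fail on labelled water, logs, urine samples or weight. All of this is true. It limits what can be claimed about frequency. It does not change the fact that removal before day 88 leaves the primary outcome unmeasured, or that EX has a large additional set of instructions to miss.

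Several stronger readings are tempting, and the protocol does not support them:

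- **That primary data are thrown away.** They are not. The loss is of data never collected.
- **That low enrichment removes participants, or does so unevenly.** It prompts encouragement and then a discussion, on the same monitoring in both groups.
- **That catheter failure is unbalanced by arm.** Nothing shows this. At Visit 4 a failed microdialysis catheter follows the biopsy and costs no primary sample.
- **That the effect is inflated by a fixed proportion.** The ratio 1/(1 − q) gives 11% at q = 0.10 and 25% at q = 0.20, but only if non-adherers gain nothing, all are removed and their prognosis is otherwise the same. Under that model a null effect stays null, so it does not measure false-positive risk.
- **That the trial becomes underpowered.** Nothing places PI withdrawals outside the 17% allowance, and the power loss is modest unless losses go well beyond it.

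It is also fair to say that inviting removed participants back yields a comparable 'f' only if they kept taking labelled water. The fix has to address that.

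**Conclusion.** The point holds in a limited form. The protocol permits post-randomisation removal from the whole study for undefined non-compliance and for procedures that do not bear on the primary outcome. Its own statement that "keeping these participants in the analysis is essential for study validity" cannot be honoured for anyone removed before day 88. Selective loss through the instructions ground is the main concern. The avoidable loss from a failed microdialysis catheter at Visit 2 is secondary, and no imbalance by arm is claimed for it.

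Under the stated assumptions the bias is about 0.3 to 1.3 points of 'f' in favour of exercise, with type I error of about 5.5% to 13%. With 6 removed the figures are 0.5 to 0.9 points and about 6% to 9%. The number removed and the correlation are assumed, and the size scales with both. If few are removed, or adherence is unrelated to outcome, the effect is small. A later analysis plan cannot recover a biopsy that was never taken, so the correction belongs in the protocol. It should be made, although it does not undermine the design.

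**What to change.** Reconcile the Intervention Period, Investigator Withdrawal and Withdrawn Subjects sections by separating the stopping of training, or of a single procedure, from leaving the study.

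- Participants stopped for non-safety reasons who still consent are asked to attend Visits 3 and 4 and are analysed in their assigned arm.
- A failed microdialysis catheter makes only the microdialysis outcome missing.
- Low enrichment flags only the label-based outcomes (adipocyte formation and TG turnover). snRNAseq and histology remain usable.
- The sponsor states whether labelled-water intake and urine collection go on for such participants, since 'f' and TG turnover are comparable only if labelling continues.
- Safety withdrawals stay as written.

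**Cost.** This is a change of wording, using visits already planned for the 70 participants. Some people who would have left would undergo the Visit 3 and 4 procedures, including biopsy and clamp. The estimated effect may also be smaller, because poor adherers are included. Where enrichment was low or labelling stopped, the powered outcome 'f' would still not be recovered.

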Appendix:

The following table identifies the procedures in relation to the study timeline for CTRL group:

	Screen	В	aseline						² H:	2O Inter	vention	Period					F	Follow-	-up	
					Week															
Visits	SV1	V1	V	2	1	2	3	4	5	6	7	8	9	10	11	12	V3	V	4 §	
Days		-14	-8	-7	0-6	7-13	14-20	21-27	28-34	35-41	42-48	49-55	56-62	63-69	70-76	77-83	85	87	88	
Windows	Within 28 days of V1	±2	±2		±1	±1	±1	±1	±1	±1	±1	±1	±1	±1	±1	±1	±1	±1		
Informed Consent	X																			
Eligibility Assessment	X																			
Randomization		X																		
Urine Collection (urea, nitrogen and creatinine)			X															X		
Urine Collection (pregnancy, if applicable)	X	X							X								X			
Urine Collection (toxicology)	X																			
Physical Exam + Medical History	X																			
Vital Signs	X																			
Anthropometrics	X	X															X			
Screening Blood Draw	X																			
Electrocardiogram	X																			
Surveys			X															X		
MRI		X															X			
DEXA		X							X*								X			
VO2max Test		X															X			
Overnight Stay with Standardized Meal			X															X		
7-Day Food Record Start				X												X				
7-Day Food Record Return					X												X			
Hair Collection			X															X		
WAT Biopsy				X															X	
Muscle Biopsy				X															X	
Respiratory Quotient (Hood)				X															X	
Pre-Clamp Blood Draw				X															X	

Hyperinsulinemic-euglycemic Clamp + Microdialysis				X															X
Accelerometer Provided			X													X			
Biopsy and Catheter Insertion Site Check					X														X
On-site Body Weight Measurement							X		X		X		X		X				
Weight Maintenance and Health Education							X		X		X		X		X				
² H ₂ O Pick-up					X		X		X		X		X		X				
² H ₂ O Container Return							X		X		X		X		X	X			
² H ₂ O Urine Collection					X	X	X	X	X	X	X	X	X	X	X	X			
Review Adverse Events	X	X	X	X	X	X	X	X	X	X	X	X	X	X	X	X	X	X	X

^{*}DEXA can take place between Weeks 4-6 to increase scheduling flexibility

On-site Body Weight Measurement, Weight Maintenance and Health Education, and ²H₂O activities must occur on the first day of exercise for that week.

[§]Visit 4 procedures must be done within 36-48 hours after the VO2max test

The following table identifies the procedures in relation to the study timeline for EX group:

The following table identifi	Screen		Baseline						H ₂ O and		_	ention P	eriod				Fo	llow-u	-up
			Week																
Visits	SV1	V1	V	2	1	2	3	4	5	6	7	8	9	10	11	12	V3§	V	7 4
Days		-14	-8	-7	0-6	7-13	14-20	21-27	28-34	35-41	42-48	49-55	56-62	63-69	70-76	77-83	85	8	37
Windows	Within 28 days of V1	±2	±2		±1	±1	±1	±1	±1	±1	±1	±1	±1	±1	±1	±1	±1	±1	
Informed Consent	X																		
Eligibility Assessment	X																		
Randomization		X																	
Urine Collection (urea, nitrogen and creatinine)			X															X	
Urine Collection (pregnancy, if applicable)	X	X							X								X		
Urine Collection (toxicology)	X																		
Physical Exam + Medical History	X																		
Vital Signs	X																		
Anthropometrics	X	X															X		
Screening Blood Draw	X																		
Electrocardiogram	X																		
Surveys			X															X	
MRI		X															X		
DEXA		X							X*								X		
VO2max Test		X															X		
Overnight Stay with Standardized Meal			X															X	
7-Day Food Record Start				X												X			
7-Day Food Record Return					X												X		
Hair Collection			X															X	
WAT Biopsy				X															X
Muscle Biopsy				X															X
Respiratory Quotient (Hood)				X															X
Pre-Clamp Blood Draw				X															X
Hyperinsulinemic-euglycemic Clamp + Microdialysis				X															X
Accelerometer Provided			X													X			
Biopsy and Catheter Insertion Site Check					X														X

IRBNet #: 1805407 Page 41 of 42 Current Version Date: 2/5/2024

Supervised Exercise Training					X	X	X	X	X	X	X	X	X	X	X	X			
On-site Body Weight					X	X	X	X	X	X	X	X	X	X	X	X			
Measurement																			
Weight Maintenance and Health					X	X	X	X	X	X	X	X	X	X	X	X			
Education																			
² H ₂ O Pick-up					X		X		X		X		X		X				
² H ₂ O Container Return							X		X		X		X		X	X			
² H ₂ O Urine Collection					X	X	X	X	X	X	X	X	X	X	X	X			
Review Adverse Events	X	X	X	X	X	X	X	X	X	X	X	X	X	X	X	X	X	X	X

^{*}DEXA can take place between Weeks 4-6 to increase scheduling flexibility

On-site Body Weight Measurement, Weight Maintenance and Health Education, and ²H₂O activities must occur on the first day of exercise for that week.

Weight Maintenance and Health Education will occur as needed following body weight measurement.

Visit 3 must be done 48-72 hours after the last exercise session. Visit 4 must be done within 36-48 hours after the VO2max test.

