⁶**Randomization**: Once a participant passes screening, completes the VO₂max test, and is considered eligible to continue in the study, they will be randomized in a 1:1 ratio into either the control (CTRL) group or the exercise group (EX). Randomization will be conducted by a statistician.

Baseline Period – Visit 2 (V2)

Day-8 (± 2): In patient. Participants will report to the local site the evening of day -8 for an overnight stay. A single urine collection will be done for measurements of urea, nitrogen, and creatinine. Participants will then receive a standardized dinner meal (10 kcal/kg; 50% carbohydrate, 15% protein, 35% fat), and be strongly encouraged to consume all food provided. Any unconsumed food will be recorded. Participants will remain fasting from completion of evening dinner meal at the local site until WAT biopsy and hyperinsulinemic-euglycemic clamp protocol are completed the following day.

¹Surveys (Optional):

With the exception of the Diet History Questionnaire (DHQ) III, all surveys will be administered to participants via the password protected computer-based software REDCap.

- **Diet History Questionnaire (DHQ) III:** Approximate duration: 10 min; the DHQ-III, owned by the NIH National Cancer Institute will be completed through the NIH-developed secured platform specific for this instrument. Participants will complete the DHQ-III under their assigned PID during the clinic visit and no personal identifiers will be obtained.
- Retrospective Visual Analog Scale (VAS): Approximate duration: 5 min; an 8-item retrospective VAS assessing appetite, including hunger, fullness after meals, thoughts of food, cravings, and urges to eat.
- Three Factor Eating Questionnaire (TFEQ): Approximate duration: 5 min; an 18item questionnaire assessing cognitive and behavioral components of eating and comprises 3 different scales corresponding to cognitive restraint, emotional eating, and uncontrolled eating.
- **Food-Craving Inventory (FCI):** Approximate duration: 5 min; a 33-item self-report measure of general and specific food cravings relating to overeating and binge eating.
- MacArthur Socioeconomic Status Index: Approximate duration: 6 min; an 11-item questionnaire regarding participants' perception of their socioeconomic status relative to their community and country, their living situation, level and degree of education obtained, job status, income, and debt.

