Accelerometers: Following the last bout of exercise training, participants will be provided with a triaxial activity monitor (Actigraph GT3X) which will be worn for 7-10 days. The monitor integrates motion sensor data from the tri-axial accelerometer to estimate the energy cost of free-living activity. The participant will wear the monitor at all times, except while showering or bathing. After the period of wear time, the participant will return the monitor and the data will be uploaded.

7-Day Food Record: Participants will be asked to record their food intake for 7 days during Week 12 and return the form at Visit 3.

Follow-up Period – Visit 3

Day 85 (±1): Outpatient. Approximate visit time: ~3-4 hours. Scheduled 48-72 hours after the last exercise bout.

The following assessments will be performed as described in **Baseline Period – Visit 1**:

¹Anthropometrics including height, weight, waist circumference, and BMI.

²Vital signs (respiratory rate, temperature, heart rate, blood pressure)

³MR assessment of visceral and subcutaneous fat (VAT/SAT) and thigh fat (~1 hour)

Current Version Date: 08/05/2024 IRBNet #: 1805407
Page 24 of 42

⁴Dual Energy X-Ray Absorptiometry (DEXA)

⁵Maximal Oxygen Consumption

Follow up Period – Visit 4

The following assessments will be performed as described in **Baseline Period – Visit 2**:

Day 87 (± 2): In patient. Participants will report to the local site the evening of day 87 for an overnight stay. Urine collection will also be done for measurements of urea, nitrogen, and creatinine. Participants will then receive a standardized dinner meal (10 kcal/kg; 50% carbohydrate, 15% protein, 35% fat), and be strongly encouraged to consume all food provided. Any unconsumed food will be recorded. Participants will remain fasting from completion of evening dinner meal at the local site until WAT biopsy and hyperinsulinemic-euglycemic clamp protocol are completed the following day.

¹Surveys (Optional)

- Diet History Questionnaire (DHQ) III
- Retrospective Visual Analog Scales (VAS)
- Three Factor Eating Questionnaire (TFEQ)
- Food-Craving Inventory (FCI)
- Perceived Stress Scale (PSS)
- MacArthur Socioeconomic Status Index
- Generalized Anxiety Disorder 7-item (GAD-7) scale
- Center for Epidemiological Studies-Depression Scale (CES-D)

```
Hair Collection (Optional)
```

Day 88 (\pm 2): Early morning.

³WAT Biopsies

⁴Muscle Tissue Biopsies (Optional)

⁵Hyperinsulinemic-euglycemic Clamp

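### The nominal follow-up days put the Visit 4 biopsy and clamp more than 48 h after the VO2max test, against the protocol's own 36-48 h rule, and the Visit 4 window differs between text and tables

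*Protocol*

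**What the plan says.** **Follow-up text.** The VO2max test belongs to Visit 3: "Day 85 (±1): Outpatient. Approximate visit time: ~3-4 hours. Scheduled 48-72 hours after the last exercise bout". The next visit is described as "Day 87 (± 2): In patient. Participants will report to the local site the evening of day 87 for an overnight stay". The adipose and optional muscle biopsies, clamp, microdialysis, blood draw and RQ follow early in the morning of Day 88, also with a ±2 day window. Neither visit description limits the time from the VO2max test to these procedures.

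**Appendix tables.** The CTRL footnote reads "Visit 4 procedures must be done within 36-48 hours after the VO2max test". The EX footnote reads "Visit 4 must be done within 36-48 hours after the VO2max test". The CTRL table shows Visit 3 on Day 85 and Visit 4 on Days 87 and 88. Both tables give Visit 4 a ±1 day window.

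**Baseline.** The VO2max test is at Visit 1, Day -14 (±2). For Visit 2, "Participants will report to the local site the evening of day -8 for an overnight stay", with biopsy and clamp early on Day -7. No VO2max-to-biopsy limit is stated for baseline.

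**Analysis.** The Statistical Analysis Plan section names paired pre-post tests (paired t or Wilcoxon signed-rank). Sample Size Determination, in contrast, is framed as a CTRL versus EX difference in change.

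**The concern.** The 36-48 h requirement is worded as mandatory, yet the calendar in the same document cannot meet it as printed. Staff who schedule from the visit text will not see the rule at all and will work to a ±2 day window. Staff who schedule from the tables will see the rule and a ±1 day window, but the day numbers beside them break the rule.

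The result is protocol deviations built into the schedule and an uncontrolled spread in hours since a maximal exercise test. The measures exposed are those taken at a single time at Visit 4: whole-body insulin sensitivity from the clamp, fasting and insulin-suppressed FFA, microdialysis lipolysis, and gene expression in adipose tissue and muscle. The protocol itself treats recovery time as important, since it sets hour limits both for Visit 3 after the last training session and for Visit 4 after the VO2max test.

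**Working it through.** **Inputs from the protocol.** VO2max on Day 85 (±1). Admission on the evening of Day 87. Biopsy, clamp and microdialysis early on Day 88. Visit 4 window ±2 (text) or ±1 (tables). Required interval 36-48 h. Baseline VO2max on Day -14, biopsy and clamp on Day -7.

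**Assumed, because the protocol gives only evening and early morning.** VO2max at clock time *t* between 08:00 and 16:00, biopsy at 07:00, admission at 18:00.

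**Formula.** Interval in hours = 24 × (day of procedure − day of VO2max) + (clock time of procedure − clock time of VO2max).

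1. *Can the nominal days give 36-48 h?* The interval is 24 × (88 − 85) + 7 − *t* = 79 − *t*. This is 71 h at *t* = 8 and 63 h at *t* = 16, or 15-23 h over the limit.

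2. *Does that depend on the assumed times?* The size does; the breach does not. Days 86 and 87 are two complete days, 48 h, between the two events. Any remaining time on Day 85 and any elapsed time on Day 88 adds to that. With VO2max at any hour and biopsy between 06:00 and 09:00, the range is 54-81 h.

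3. *Does counting Visit 4 from admission help?* The EX footnote, which refers to the visit and not to its procedures, might be read that way. The interval is 24 × (87 − 85) + 18 − *t* = 66 − *t*, or 50-58 h. It falls to 48 h only if the VO2max test is at the clock hour of the evening admission or later.

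4. *Which gaps comply?* Under the assumed times:

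| Calendar-day gap, VO2max to biopsy | Interval | Within 36-48 h |
|---|---|---|
| 1 | 15-23 h | no |
| 2 | 39-47 h | yes |
| 3 (nominal) | 63-71 h | no |
| 4 | 87-95 h | no |

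Write *a* for the shift of Visit 3 and *b* for the shift of Visit 4, in days. The gap is 3 + *b* − *a*, so compliance needs *b* − *a* = −1. With ±1 for both visits (tables) there are 3 × 3 = 9 combinations, and 2 comply: (0, −1) and (1, 0). With ±1 and ±2 (text) there are 3 × 5 = 15, and 3 comply: those two and (−1, −2). None leaves both visits on their nominal days.

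5. *Windows.* Visit 1, Visit 2 and Visit 3 agree between text and tables. Only Visit 4 differs.

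6. *Baseline, for comparison.* 24 × 7 + 7 − *t* = 175 − *t*, or 159-167 h: about 7 days.

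**The case against.** The best defence is that a footnote saying must can be read as narrowing the day windows. VO2max on Day 85 with biopsy on Day 87, or VO2max on Day 86 with biopsy on Day 88, satisfies the rule inside ±1 day. This stands: the schedule is contradictory, not unworkable, and a reader who infers that no participant can comply goes too far. It does not remove the contradiction, because the nominal day is what a site aims for and the visit text never mentions the rule.

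A reader might also infer bias in every pre-post contrast, including the powered outcome. The documents do not support that. Adipocyte formation and TG turnover come from deuterium taken in over 12 weeks (84 days), so a one-day shift in biopsy is about 1/84, or 1.2%, of the labelling period. Both arms share the nominal days and the rule, so a common shift largely cancels in a between-arm comparison. It does not cancel in the paired tests that the protocol names. The documents give no figure for how long a maximal test affects the acute measures, so no size of bias can be stated.

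Finally, a reader might call the 7-day baseline interval a second contradiction. It is not: the 36-48 h rule is attached to Visit 4 only. Wide ranges built from the windows alone, such as 0-6 days, also mislead. They ignore the rule, and the 0-day case would put Visit 4 admission before Visit 3.

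**Conclusion.** The protocol is wrong as written on this point. Its nominal follow-up days break its own mandatory interval at any clock time, the Visit 4 window is stated in two ways, and the rule is missing from the text that describes the visits. The excess over 48 h is certain for a participant on the nominal days. Its size, 15-23 h, rests on the assumed clock times.

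The statistical consequence is limited. It is avoidable variation in hours since maximal exercise for the clamp, FFA, microdialysis and expression measures. The effect on the 12-week label outcomes is negligible. The difference between about 7 days at baseline and a much shorter interval at follow-up is a matter for interpreting within-arm tests of the acute measures, not an error in the plan.

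**What to change.** Reconcile the Day 85/87/88 schedule, the 36-48 h rule and the ±1 versus ±2 Visit 4 window, so that one requirement appears in the Visit 3 and Visit 4 text and in both Appendix tables, with the same wording on whether it refers to admission or to the procedures. The investigators decide which timing is right. If Visit 3 moves, the change must also be checked against its 48-72 h limit after the last exercise bout.

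Record the clock times of the VO2max test and of the start of biopsy and clamp, so that the actual hours are known for each participant. When within-arm pre-post results for the acute measures are interpreted, note the nominal baseline interval of about 7 days.

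The cost is an amendment to schedule wording, some care in booking visits, and a few clock times per participant. No procedure is added and the sample size is unaffected.
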